3.7 Treatment assignment and treatment groups

It is expected that study participants receive treatment as randomized for the Double-Blind Treatment Period, or as assigned per protocol study design (via reallocation) for the Maintenance Period.

Hence safety analyses will be based:

- on the SS as randomized, for the Double-Blind Treatment Period (displaying data under Placebo and BKZ 160mg Q4W columns),
- on the MS as assigned treatment, for the Maintenance Period (displaying data under BKZ 160mg Q4W Total column),
- on the SS as randomized/assigned treatment for the overall period (displaying data under BKZ 160mg Q4W Total column),

However, if after unblinding it is determined that study participants randomized to placebo received bimekizumab at any time during the Double-Blind-Treatment Period, then for safety analyses these study participants will be reallocated to the bimekizumab treatment group. Study participants randomized to bimekizumab will only be reallocated to the placebo treatment group if they never received bimekizumab. For AE analyses, AEs for each study participant will be summarized based on the treatment at the onset of each particular AE. AEs that occur on the day of first IMP administration will be allocated to the treatment received on that day. For study participants randomized on placebo who switch treatment per study design at Week 16 (ie, reallocation to bimekizumab treatment), AEs will be allocated to the treatment the study participant was on the day the event occurred. If the event occurs on the day of the switch, it will be attributed to the initial treatment (ie, Placebo), unless the AE fulfills the criteria for an

anaphylactic reaction in which case it will be attributed to the new treatment (ie, bimekizumab). Specifically, this includes events meeting any of the following criteria:

- Events that fulfil the anaphylactic reaction criteria for acute events (refer to [Appendix 1](#))
- Events, that fulfil the hypersensitivity reaction criteria
- Events with an HLT of 'Administration site reactions NEC'
- Events with an HLT of 'Injection site reaction'

Efficacy analyses will be performed according to randomization and not actual treatment received. That is, if after unblinding it is determined that study participants randomized to placebo received bimekizumab at any time during the Double-Blind-Treatment Period efficacy analyses for these study participants will not be reallocated to the bimekizumab treatment group.

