4.2.2 Handling of missing data for AE

For analyses of AEs, a complete date must be established to correctly identify the AE as occurring during treatment or not. For purposes of imputing missing components of partially reported start and stop dates for AEs, the algorithms listed below will be followed. In the event of ambiguity or incomplete data which makes it impossible to determine whether the AE was treatment emergent, the AE will be considered treatment emergent. If an imputed date occurs after a study participant's date of death, the imputed date will be set to the date of death.

Although the algorithms for treatment-emergence depend on the onset date, imputation rules are provided for stop date as well, as these may be needed for certain statistical analyses, such as an analyses of AE prevalence or AE duration.

Start and stop dates of AEs will be displayed as reported in the study participant data listings (ie, no imputed values will be displayed in data listings).

Imputation of Partial Start Dates

- If only the month and year are specified and the month and year of first dose is not the same as the month and year of AE onset, then use the 1st of the month

- If only the month and year are specified and the month and year of first dose is the same as the month and year of AE onset, then use the date/time of first dose
- If only the month and year are specified, and the study participant did switch treatment during that month and year, then use the date of first switch treatment.
- If only the year is specified, and the year of first dose is not the same as the year of AE onset, and if the study participants did not switch from placebo to bimekizumab at Week 16, then use January 1 of the year of AE onset
- If only the year is specified, and the year of first dose is the same as the year of AE onset, then use the date/time of first dose
- If only the year is specified, and the year of first dose is the same as the year the study participant did switch treatment, then use the date of first switch treatment.
- If only the year is specified, and the year of first dose is the same as the year of the AE onset and the same as the year the study participant did switch treatment, then use the date of first dose.
- If the imputed stop date is prior to the imputed start date
 - For missing start day and start month:

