4.2.3 Handling of missing data for prior and concomitant medications

Any medications with incomplete start and end dates/times will be handled according to the following rules for classification as prior and concomitant and for the calculation of relative study days. In the event of ambiguity or incomplete data which makes it impossible to determine whether a medication was concomitant or not, the medication will be considered as concomitant. Such imputations will only be performed for these classifications and calculations; in the listings all data will be shown as recorded on the electronic case report form (eCRF).

Imputation of Partial Start Dates

- If only the month and year are specified and the month and year of first dose is not the same as the month and year of the start date, and the study participant did not switch treatment during that month and year, then use the 1st of the month
- If only the month and year are specified and the month and year of first dose is the same as the month and year of the start, then use the date of first dose
 - If this is leading to a start date after the stop date of then use the 1st of the month
- If only the month and year are specified, and the study participant did switch treatment during that month and year, then use the date of first switch treatment.
- If only the year is specified, and the year of first dose is not the same as the year of the start date and the study participant did not switch treatment during that year, then use January 1 of the year of the start date
- If only the year is specified, and the year of first dose is the same as the year of the start date, then use the date of first dose
- If the start date is completely unknown, and the stop date is unknown or not prior to the date of first dose, then use the date of first dose
- If the imputed stop date is prior to the imputed start date
 - If the year of start date is the same as the year of first dose and the stop date is after the date of first dose then set the start date to the date of first dose
 - Otherwise set to the 1st January of the year of the start date

Imputation of Partial Stop Dates

- If only the month and year are specified, then use the last day of the month
- If only the year is specified, then use December 31 of that year
- If the stop date is completely unknown, do not impute the stop date

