10.2 Adverse events

Adverse events with start date prior to first administration of study medication are defined as pre-treatment AEs. No summaries of these events will typically be produced although they will be included in listings.

Adverse events that started more than 140 days after the last administration of study medication are defined as post-treatment AEs. Such events will not be included in any tabulated summaries but will be listed.

Treatment-emergent AEs (TEAEs) are defined as those AEs that have a start date on or following the first dose of study treatment through the final dose of study treatment + 140 days (covering the 20-week SFU period).

All summaries will be provided by treatment group. The treatment group for each study participant will be defined as the treatment received at the onset of the AE. If the onset of the AE occurs on the day where the study participant switches treatment from the Double-Blind Treatment Period to the Maintenance Period and receives a new treatment, it will be attributed to the originally randomized study treatment. The only exception to this is if the AE fulfills the criteria for an anaphylactic reaction. See Section 3.7 for further details.

AEs will be presented as “number of study participants (percentage of study participants) [number of events]”. In this style of output, “[number of events]” will include all cases of an AE including repeat occurrences in individual study participants, while “number of study participants” will count each study participant only once.

Adverse event summaries by SOC, HLT and PT will be ordered alphabetically for SOC and HLT within SOC and in terms of decreasing frequency for PT within HLT in the bimekizumab treatment group and then similarly by decreasing frequency in the placebo group.

AE summaries by PT will be ordered in terms of decreasing frequency for PT within the bimekizumab treatment group, and in the event of ties, PT will be sorted alphabetically.

Study participant time at risk represents the time a study participant is at risk for having an AE. The definitions for study participant time at risk (in days) are outlined in Section 10.1. These definitions will be used for exposure-adjusted AE summaries.

Selected AE summaries will include the exposure adjusted incidence rate (EAIR) with associated 95% confidence interval and the exposure adjusted event rate (EAER).

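### Partial-date rules charge non-excepted switch-month adverse events, and some later-year events, of placebo switchers to placebo even if they began after the switch

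*SAP*

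**What the plan says.** **Month-only onset (SAP 4.2.2).** If the reported month and year is the one in which "the study participant did switch treatment during that month and year, then use the date of first switch treatment". An earlier bullet in the same list says that if the first-dose month "is not the same as the month and year of AE onset, then use the 1st of the month". The parallel list for medications (SAP 4.2.3) limits its version to cases where "the study participant did not switch treatment during that month and year, then use the 1st of the month". The AE list has no such limit.

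**Year-only onset (SAP 4.2.2).** The bullet that leads to the switch date applies when "the year of first dose is the same as the year the study participant did switch treatment". It does not mention the year of the AE. The January 1 bullet is closed to participants who switched from placebo to bimekizumab at Week 16.

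**Attribution on the switch day.** SAP 3.7: "If the event occurs on the day of the switch, it will be attributed to the initial treatment (ie, Placebo"), unless the event meets the criteria for an "anaphylactic reaction in which case it will be attributed to the new treatment (ie, bimekizumab"). The list that follows names four classes: acute anaphylactic events, hypersensitivity events, and events coded to the two high-level terms for administration-site and injection-site reactions. SAP 10.2 repeats the default: "it will be attributed to the originally randomized study treatment".

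**Tables.** Sections 3.7 and 10.2 and Table 4-3 show AEs for the Maintenance and Overall periods under the bimekizumab total only. A placebo column exists only for the Double-Blind Treatment Period.

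**The concern.** A convention for a known same-day onset is reasonable: on the day of the first bimekizumab injection, most events are more plausibly carried over from placebo. But neither 3.7 nor 10.2 separates an onset reported on that day from one placed there by imputation. The same-day convention therefore decides the treatment for every ordinary AE whose start day in the switch month is missing, including those that began weeks into bimekizumab. Separately, the year-only bullets can give an onset date outside the year that the site reported, or no date at all. At stake is the completeness of the bimekizumab AE counts among participants who switched.

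**Working it through.** The plan states no figure on this point, so the check traces its rules.

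**Step 1: month-only onset in the switch month.** The switch is at Week 16, 112 days after first dose with a 3-day visit window. Taking first-dose dates over one year and switch offsets of 109 to 115 days gives 366 × 7 = 2,562 cases. In none do first dose and switch share a calendar month, so the first-dose-month bullet never interferes. Two bullets remain:

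| Bullet used | Imputed onset | Ordinary AE charged to | Excepted AE charged to |
|---|---|---|---|
| Switch month | switch day | placebo, all | bimekizumab, all |
| 1st of month | day 1 | placebo, all | placebo, except when the switch falls on day 1 (about 1/30.5 = 3%) |

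For an ordinary AE both bullets lead to placebo. For an excepted AE the choice of bullet decides the treatment, and the plan gives no priority.

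**Step 2: how many of these began after the switch.** The plan does not say. If onset is uniform within the month and the switch day is equally likely to be any day (assumptions, not plan figures), the share starting strictly after the switch day in a month of L days is (L − 1)/(2L). For L = 30 this is 29/60 = 48.3%; for L = 31 it is 30/62 = 48.4%. The enumeration gives 48.4%. So about 48% of such events would begin after the switch day, while 0% of the ordinary ones are charged to bimekizumab.

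**Step 3: year-only onset in a switcher.** Illustrative dates, read against the bullets of 4.2.2:

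| First dose | Switch | AE reported as | Bullet that applies | Result |
|---|---|---|---|---|
| Mar 2019 | Jul 2019 | 2019 | explicit tie-break | first dose, placebo |
| Oct 2019 | Feb 2020 | 2019 | first-dose year = AE year | first dose, placebo (correct) |
| Mar 2019 | Jul 2019 | 2020 | switch bullet only | Jul 2019; placebo unless excepted |
| Oct 2019 | Feb 2020 | 2020 | none | no date defined |

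In the third row the AE is dated before its own reported year and charged to placebo, although it certainly began after the first bimekizumab dose. With participation of up to 73 weeks (SAP 2.3), an AE in the calendar year after first dose is ordinary. In the fourth row no bullet applies, yet 4.2.2 itself requires a complete date.

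**Step 4: where the events go.** An event charged to placebo cannot enter a table that has only a bimekizumab column. The ordinary events of Step 1 and the third-row event of Step 3 are therefore absent from the Maintenance and Overall AE tables.

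**The case against.** Four points can be made in the plan's defence.

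- The switch-day convention is explicit, consistent between 3.7 and 10.2, and carries an exception for acute reactions. That stands. A reader might infer that ambiguous events always leave the bimekizumab tables; the documents do not support this. The four excepted classes go to bimekizumab on the switch day, and under the switch-month bullet that includes any that began on placebo. Participants randomised to bimekizumab never change treatment, so none of their events move.
- A reader might also say that the plan breaks its own worst-case principle. Section 4.2.2 has no such principle for attribution. Its ambiguity default concerns treatment emergence only, and its other defaults concern intensity, relationship and, at the final analysis, seriousness.
- Charging all month-only events to bimekizumab would also misattribute about half under the uniform assumption. This is true and is a cost of the fix, but it does not defend dates outside the reported year or a case with no rule.
- Some visibility exists. Section 10.2.1 plans a listing of AEs on the day of first study drug, including the first bimekizumab injection at Week 16 for placebo participants, and listings show dates as reported. This does not correct the tables, and the plan does not say whether imputed dates feed that listing.

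A further tempting reading is that these events vanish from every table, because Section 3.2.2.1.1 ends the safety double-blind period before the switch day. The text does not settle this. That section refers to 3.7 for AEs on the day of IMP administration, and 3.7 assigns a treatment but names no period table.

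**Conclusion.** The point holds for placebo participants who switch, about 100 planned of 300. Their non-excepted AEs with a missing start day in the switch month are charged to placebo under either applicable bullet (under the 1st-of-month bullet, a switch on the 1st simply makes the two dates coincide). They are therefore kept out of the Maintenance and Overall AE tables. The year-only bullets contain one plain error (the AE year is ignored) and one gap.

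The size of any bias cannot be taken from the plan: it gives no count of partial dates, and the number is probably small. The 48% rests on the uniform-onset assumption and describes only events with a missing day in the switch month. For ordinary events the direction is towards fewer bimekizumab events; for the excepted classes it depends on which of the two month-only bullets is applied. No efficacy result or multiplicity-controlled test is touched. This is a low-severity wording defect that is worth correcting because the rules as written give wrong dates and attributions.

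**What to change.** 1. **Year-only bullets (4.2.2).** Compare the AE onset year with the switch year. If the AE year is later than the switch year, use January 1 of the AE year. If it equals the switch year but not the first-dose year, use the switch date. The reworded bullets should also cover a switcher's AE reported in a year before first dose, because the January 1 bullet now excludes all switchers.
2. **1st-of-month bullet (4.2.2).** Add the condition already used in 4.2.3, that no switch took place in that month and year. This removes the conflict between the two month-only bullets. Without it, the third change would not be triggered whenever the 1st of the month is used.
3. **Switch-day attribution (3.7 and 10.2).** Limit the default to placebo to completely reported onset dates. Charge an AE whose start was imputed to the switch date to bimekizumab, unless a reported stop date before the switch shows that it began on placebo.

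It would also help to state which period table receives a switch-day event that is charged to placebo.

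The cost is SAP wording and a small change to the date-imputation and attribution programs; no new data are needed. The downside is that some events that began on placebo will be counted to bimekizumab, so its counts may rise slightly.

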3.2.2.1.1 Study periods for safety data

The following study periods are defined for the classification of safety data by study period:

- Pre-treatment Period (Screening Period): Starts at the time of the informed consent date and ends prior to the day and time of the first dose administration of study drug.
- 16-Week Double-Blind Treatment Period (DBTP): Starts on the day of the first IMP administration and ends prior to the day of first IMP administration in the maintenance period (first IMP in the MP typically occurs at Week 16, but for those that miss the Week 16 IMP, first IMP in the MP will be the first IMP administration after Week 16). For study participants that withdraw from the study prior to start of IMP in the maintenance period, the DBTP ends on the day of the ET Visit.

See Section 3.7 (Treatment assignment and treatment groups) for allocation of AEs that occur on the day of IMP administration.

For vital sign parameters, the DBTP will start at the day and time of first IMP administration and ends prior to the day and the time of first IMP administration in the MP as there are 3 assessments collected at Baseline and Week 16 (one pre-dose, one 30 minutes post-dose and one 1-hour post-dose).

- 36-Week Maintenance Treatment Period (MP): Starts on the day of IMP administration at the Week 16 visit and ends 28 days (one dosing interval) after the day of last IMP administration before the Week 52 visit. For participants that do not receive IMP at the Week 16 visit, the MP starts on the day of first IMP administration after Week 16. For study participants that

withdraw from the study after Week 16 but before Week 52, the MP ends on the day of the ET Visit. In the event that no ET visit is performed, the MP ends 28 days after the last IMP administration.

For vital sign parameters, the day and the time will be used to define the MP for the same reason that given above.

- **Safety Follow-Up Period:** The SFU period will be defined for all study participants who complete the final IMP administration of the study at Week 48 and do not enter the OLE study, or for study participants who discontinue early including those withdrawn from IMP.
 - For study participants who complete the final IMP administration of the study at Week 48 and do not enter the OLE study, the SFU period starts 29 days after the day of last IMP administration before the Week 52 visit and ends on the day of the SFU Visit or on the last contact date, whichever happens later.

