Note: If the date of last dose + 28 extends to a date beyond the final visit date (not including SFU), then this calculation reverts to:

$$\text{Date of last visit (not including SFU)} - \text{Date of first dose} + 1$$

- For study participants who die during the DBTP, this calculation reverts to:

$$\text{Date of death} - \text{Date of first dose (DBTP)} + 1$$

- The time at risk during the DBTP will be calculated as follows:

- For study participants who complete the final visit of the DBTP and continue to the Maintenance Period:

$$\text{Date of first dose (MP)} - \text{Date of first dose (DBTP)} + 1$$

- For study participants who discontinue on or prior to the final visit of the DBTP (ie, Week 16), use the minimum of the following:

- Total number of days in the DBTP:

- For those that discontinue prior to the Week 16 visit, use 112 days,
 - For those that discontinue at the Week 16 visit, use the total number of days based on Week 16 visit date, which can be a maximum of 115 days due to visit windows

- $$\text{Date of last clinical contact} - \text{Date of first dose (DBTP)} + 1$$
, last clinical contact can be defined as last scheduled site visit.

- For study participants who die during the DBTP, then this calculation reverts to:

$$\text{Date of death} - \text{Date of first dose (DBTP)} + 1$$

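### AEs starting on the Week 16 dosing day, acute reactions apart, follow a different rule in each arm: either placebo gains a day in the double-blind AE tables, or its events on that day appear in no table

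*SAP*

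**What the plan says.** - **Period boundary (SAP 3.2.2.1.1).** The safety double-blind period (DBTP) is defined thus: "Starts on the day of the first IMP administration and ends prior to the day of first IMP administration in the maintenance period". The Maintenance Period (MP): "Starts on the day of IMP administration at the Week 16 visit". Neither definition distinguishes the arms. The section then points elsewhere: "See Section 3.7 (Treatment assignment and treatment groups) for allocation of AEs that occur on the day of IMP administration".
- **Treatment attribution (SAP 3.7).** For participants who move from placebo to bimekizumab: "If the event occurs on the day of the switch, it will be attributed to the initial treatment (ie, Placebo". The sentence goes on to an exception for an "anaphylactic reaction in which case it will be attributed to the new treatment (ie, bimekizumab". The list that follows widens this to hypersensitivity reactions and two site-reaction terms, the last being "Events with an HLT of 'Injection site reaction".
- **Restatement (SAP 10.2).** If onset falls on the day a participant changes to a new treatment, "it will be attributed to the originally randomized study treatment", with the same exception by reference to 3.7.
- **Displays (SAP 10.2 and Table 4-3).** AE tables have Placebo and bimekizumab columns for the DBTP only. The MP and overall tables show a single bimekizumab total column.
- **Time at risk (SAP 10.1.1 to 10.1.3).** Section 10.1.1 has one formula, headed "For study participants who complete the final visit of the DBTP and continue to the Maintenance Period": first MP dose minus first DBTP dose plus 1. Section 10.1.2 counts from the first MP dose, again plus 1. Section 10.1.3 subtracts a day from the DBTP part for participants who switch.

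**The concern.** The switch-day rule is written only for participants who receive a new treatment. Someone on bimekizumab throughout does not switch, so the period definition alone places that person's Week 16 dosing-day AE, and it puts it in the MP. A placebo participant's AE on the same day is attributed to Placebo, and the only tables with a Placebo column are the DBTP tables.

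The DBTP tables, and the risk differences for the safety topics of interest in 10.2.2, are the trial's only placebo-controlled AE comparison. A boundary rule that differs by arm does not belong there, even if its effect is small. The SAP sets an arm-neutral boundary for other data: Week 16 vital signs before the dose belong to the DBTP and those after it to the MP, and Week 16 efficacy assessments belong to the DBTP.

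**Working it through.** **Plan's own day counts.** 16 × 7 = 112 days, and 112 + 3 (visit window) = 115. These are the 112 and 115 days in 10.1.1 for participants who discontinue. Both equal the length of a DBTP that excludes the Week 16 dosing day, as 3.2.2.1.1 defines it.

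**Where a Week 16 dosing-day AE goes (outside the exception).**

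| | Period (3.2.2.1.1) | Treatment (3.7, 10.2) | Table |
|---|---|---|---|
| Bimekizumab throughout | MP | Bimekizumab | MP and overall |
| Placebo switcher, reading A: attribution keeps it in the DBTP | DBTP | Placebo | DBTP |
| Placebo switcher, reading B: period definition is strict | MP | Placebo | None (MP and overall have no Placebo column) |

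Under A the nominal event window is 113 days on placebo and 112 on bimekizumab. Under B it is 112 in both, but a treatment-emergent placebo event is not tabulated.

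**Size under A, uniform hazard.** Share of events on the extra day = 1/113 = 0.9%. Window ratio = 112/113 = 0.991; with the ±3-day visit window it runs from 109/110 = 0.991 to 115/116 = 0.991.

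Crude incidence with equal constant hazards: if the 113-day incidence is p, the 112-day incidence is 1 − (1 − p)^(112/113).

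| p (113 days) | 112 days | Difference (points) | Participants of 200 |
|---|---|---|---|
| 5% | 4.96% | 0.04 | 0.09 |
| 20% | 19.84% | 0.16 | 0.32 |
| 40% | 39.73% | 0.27 | 0.54 |
| 60% | 59.67% | 0.33 | 0.65 |

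**If onsets cluster (assumed, not in the SAP).** With k times the average daily hazard on that day, the share is k/(112 + k): 5/117 = 4.3% for k = 5 and 10/122 = 8.2% for k = 10. For p from 5% to 60%, crude incidence then differs by 0.2 to 1.6 points (k = 5) or 0.4 to 3.1 points (k = 10).

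**Time at risk, nominal visits, participant entering the open-label extension** (Week 52 = 52 × 7 = 364 days after first dose):

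- 10.1.1, DBTP, both arms: 112 + 1 = 113 days.
- 10.1.2, MP: 364 − 112 + 1 = 253 days.
- 10.1.3, combined, bimekizumab throughout: 364 + 1 = 365 days.
- 10.1.3, DBTP part for a placebo switcher: 112 − 1 + 1 = 112 days.

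The period figures for a bimekizumab participant add to 113 + 253 = 366, one more than the combined 365, because the Week 16 day is counted twice. For a placebo switcher 10.1.3 gives 112 + 253 = 365. The placebo DBTP is therefore 113 days under 10.1.1 and 112 under 10.1.3. With 113 days at risk and 112 days of countable events, the bimekizumab DBTP event rate is multiplied by 112/113 = 0.991.

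**The case against.** The strongest reply is that 3.7 and 10.2 assign events to a treatment, not to a period, and that 3.2.2.1.1 closes the DBTP before that day for everyone. No sentence says that a placebo switch-day event stays in the DBTP. This stands, and it is why a one-sided bias cannot be taken as shown: the tilt exists only under reading A. Reading B is no defence, however, because it leaves treatment-emergent events out of every table. The listings, including the one of AEs on first-dose days, would still show them.

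Four further limits hold.

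- A reader might take the rule to cover all AEs. It does not: acute reactions on that day leave the placebo column too, so the arms match for them, including the hypersensitivity safety topic.
- A reader might infer that bimekizumab events are lost. In crude incidence bimekizumab keeps its full 16 weeks and placebo gains a day; the bimekizumab events are tabulated in the MP and overall tables. Only the exposure-adjusted rates charge bimekizumab for a day without countable events.
- A reader might reason that Week 16 is one of five or six post-Baseline visits, so that 17% to 20% of visit-detected AEs would move. The SAP classifies AEs by onset date. It does not date examination findings to the visit, and it gives no share of visit-dated AEs. Participants are also counted once, so losing one event need not change incidence.
- Section 4.2.2 imputes month-only onsets in the switch month to the switch date, which can add placebo onsets to that day. The SAP gives no frequency, and no net direction follows.

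**Conclusion.** The point holds as an inconsistency in the plan. For AEs outside the acute-reaction exceptions, the Week 16 dosing day is handled differently by arm, and neither reading both tabulates every event and treats the arms alike. Under reading A the comparison is tilted towards bimekizumab by about 0.9% of events, or less than one participant in 200 for incidences between 5% and 60%. This assumes equal, constant hazards and nominal visit days. A larger effect needs onsets to cluster on that day, and nothing in the SAP establishes this. Under reading B there is no tilt, but some placebo events are missing from the tables. The time-at-risk inconsistency does not depend on the reading. All of this is small, but programmers would have to choose between conflicting sections for the only controlled safety comparison.

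**What to change.** State one rule for both arms in 3.2.2.1.1, 3.7 and 10.2: an AE starting on the day of the first maintenance dose belongs to the DBTP and to the randomised treatment. The acute-reaction categories listed in 3.7 remain the exception and go to the MP and bimekizumab in both arms.

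Align 10.1.1, 10.1.2 and 10.1.3 so that the day is counted once and in the same period for both arms. With the day in the DBTP, the 113-day formula in 10.1.1 stands, MP time at risk starts the day after, and the subtraction of a day for switchers in 10.1.3 goes. A footnote should say that the excepted acute reactions of that day are shown in the MP. Table 4-3, which runs DBTP tables up to Week 16 and MP tables from Week 16, should carry the same boundary.

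The cost is SAP wording, one programming condition for AE period assignment and the matching edits to the time-at-risk derivations. No data collection changes.
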